#### Last observation carried forward – Rescue observed cases (LOCF-ROC)

Any values taken after rescue medication intake will be kept. LOCF (as described above) will be applied thereafter.

The following table provides an overview of the different approaches.

Last observation carried forward - ALL (LOCF-ALL)

All available data will be considered, including values obtained on treatment and post-treatment. Any values taken after rescue medication intake will be kept.

Missing values will be replaced by LOCF (including interpolation for a missing value within a course of measurements).

Table 6.6: 1 Summary of imputation methods for diabetes related endpoints

Imputation method	Endpoint	Handling of missing values	Handling of values after rescue therapy
OC	Continuous endpoints	No imputation	Excluded (considered missing)
LOCF	HbA1c (at each visit and change from baseline)	Missing values following the last on-treatment value are replaced by the last on-treatment value. Missing values with subsequently available on-treatment values are imputed by interpolation. Baseline values are not carried forward, but will be used in interpolation.	Values after the start of rescue therapy are replaced by the last available on-treatment measurement. If no on-treatment HbA1c measurement prior to rescue therapy is available baseline values are carried forward.
	Other continuous endpoints	As for HbA1c.	Values after the start of rescue therapy are replaced by the last available on-treatment measurement. If no on-treatment measurement prior to rescue therapy is available baseline values are not carried forward and consequently, in this case values in the LOCF analysis are missing.
OC-ROC	Continuous endpoints	No imputation	Included
LOCF-ROC	All continuous endpoints	As for LOCF of HbA1c.	Included

Pro-insulin, C-peptide, antibodies

Only patients with available baseline values will be presented descriptively. Missing values will not be replaced.

### Binary key secondary endpoints and binary tertiary diabetes related endpoints

#### *Binary diabetes related endpoints including the restriction as of being on treatment*

If a patient was off-drug before trial stop, without re-start, or already died prior to regular completion, the patient will be handled as non-completers considered failure (NCF).

For further details refer to [Section 7.5.1](#).

#### *Binary diabetes related endpoints including HbA1c and/or weight*

If a patient did not permanently and prematurely discontinue from treatment and has a missing value of HbA1c and/or weight at the last on-treatment visit, the missing value will be imputed by LOCF-ROC (weight)/LOCF (HbA1c).

If a patient has a missing value for weight at week 16 (corresponding to visit 6), the latest value before the week 16 window start will be used.

For the sensitivity analysis of the second and third key secondary endpoints on the OS patients who prematurely discontinue study treatment will not be counted as non-responders. Instead, their last on-treatment value will be used.

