## 5. VARIABLES AND THEIR ASSESSMENT

### 5.1 EFFICACY

#### 5.1.1 Endpoint(s) of efficacy

The primary endpoint in this trial is time to the first occurrence of any of the following adjudicated components of the primary composite endpoint: CV death (including fatal stroke and fatal MI), non-fatal MI (excluding silent MI) or non-fatal stroke

The key secondary efficacy endpoints are:

- time to the first occurrence of any of the following adjudicated components of CV death (including fatal stroke and fatal MI), non-fatal MI (excluding silent MI), non-fatal stroke or hospitalisation for unstable angina pectoris
- composite endpoint of (treatment sustainability defined as the proportion of patients that are on study treatment at study end, that at Final Visit maintain glycaemic control ( $HbA_{1c} \leq 7.0\%$ ) without need for rescue medication (between end of titration [Visit 6] and Final Visit) and patients without any moderate/severe hypoglycaemic episodes (between Visit 6 and Final Visit) and without  $> 2\%$  weight gain at Final Visit (between Visit 6 and Final Visit))
- composite endpoint of (treatment sustainability defined as the proportion of patients that are on study treatment at study end, that at Final Visit maintain glycaemic control ( $HbA_{1c} \leq 7.0\%$ ) without need for rescue medication (between Visit 6 and Final Visit) and patients without  $> 2\%$  weight gain at Final Visit (between Visit 6 and Final Visit))

Whereas moderate/severe hypoglycaemic episodes are defined as:

- Moderate hypoglycaemic event: documented symptomatic hypoglycaemia with plasma glucose concentration  $\leq 70$  mg/dL. Event accompanied by typical symptoms of hypoglycaemia but no need for external assistance
- Severe hypoglycaemic event: documented hypoglycaemic episode requiring assistance of another person to actively administer carbohydrate, glucagon or other resuscitative actions need for external assistance

Additionally secondary efficacy endpoints are the change from baseline of  $HbA_{1c}$ , FPG, proportion of patients that at Final Visit maintain glycaemic control without need for rescue medication (between end of titration [Visit 6] and Final Visit) to obtain  $HbA_{1c} \leq 7.0\%$  or that obtain  $HbA_{1c} \leq 7.0\%$  overall (see Section [7.1](#)).

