### Last observation carried forward (LOCF)

Any values taken after rescue medication intake will be set to missing. The last observed on-treatment value (within the time window from first drug intake until last permanent treatment stop date plus the endpoint specific follow-up time) will be carried forward, whether or not it is selected/picked as the value for the respective previous week (if multiple measurements were performed within a time window for a visit, as described in [Section 6.7.3](#)). That means, for patients receiving rescue therapy the last on-treatment measurement prior to the intake of rescue therapy will be carried forward. Missing values before baseline will not be imputed.

One missing value within a course of measurements on treatment will be interpolated based on the last observed value before the missing visit and the first observed value after the missing visit.

(This is independent from the selection of a value as the picked visit value to be used in the descriptive analysis by week, as described in [Section 6.7.3](#)).

Interpolation will be done according to the formula described below. Let:

$D_0$  = date of a visit with a missing value for an endpoint;

$D_1$  = date of the next visit, with endpoint value non-missing, after the visit with missing value;

$D_{-1}$  = date of the previous visit, with endpoint value non-missing, before the visit with missing value;

$E_i$  = endpoint values for visits  $D_{-1}$ ,  $D_0$ ,  $D_1$  for  $i = -1, 0$  and  $1$ .

Then the missing value will be interpolated as:

$$E_0 = E_{-1} + \left( (E_1 - E_{-1}) \times \frac{D_0 - D_{-1}}{D_1 - D_{-1}} \right)$$

Replacement of missing values will be performed for all weeks up to the last planned week that could have been reached by a patient, based on individual randomisation into the trial. Refer to [Section 7.5.1](#) for the definition of this planned final visit.

In general baseline results will not be carried forward in case of missing on-treatment values, but can be used for interpolation.

Only, if a patient receives rescue therapy before the first available on-treatment HbA1c measurement, the HbA1c baseline value will be carried forward.

For all other parameters, except HbA1c, no baseline values will be used to replace post rescue measurements.

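### In the HbA1c ≤ 7.0% overall endpoint, a rescued patient who misses only the last HbA1c is scored on a pre-rescue or baseline value

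*SAP*

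**What the plan says.** The rule is in SAP Section 6.6, in the part on binary diabetes endpoints that use HbA1c or weight. It applies where a patient "has a missing value of HbA1c and/or weight at the last on-treatment visit, the missing value will be imputed by LOCF-ROC (weight)/LOCF (HbA1c". Its opening condition is "If a patient did not permanently and prematurely discontinue from treatment", so it reaches only patients who stayed on study drug. It does not replace a last value that was observed.

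The same section defines both methods.

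- **Plain LOCF:** "Any values taken after rescue medication intake will be set to missing", and "for patients receiving rescue therapy the last on-treatment measurement prior to the intake of rescue therapy will be carried forward". For HbA1c alone, "if a patient receives rescue therapy before the first available on-treatment HbA1c measurement, the HbA1c baseline value will be carried forward". Table 6.6: 1 repeats this: "If no on-treatment HbA1c measurement prior to rescue therapy is available baseline values are carried forward".
- **LOCF-ROC:** "Any values taken after rescue medication intake will be kept. LOCF (as described above) will be applied thereafter".

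Protocol Section 5.1.1 lists the "proportion of patients that at Final Visit maintain glycaemic control without need for rescue medication" at a threshold of 7.0%. The same sentence then adds the proportion reaching that threshold *overall* and refers to Section 7.1. SAP Section 7.5.2.2.3 gives the test, the logistic regression and the interval method for binary diabetes endpoints, but no separate imputation rule.

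**The concern.** An endpoint that ignores rescue should use HbA1c values measured after rescue. The imputation rule throws them away. Two patients with the same rescue date and the same HbA1c history can be scored differently because one of them missed the final blood draw. The first is scored on the observed value, the second on a value from before rescue or from before randomised treatment.

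The *overall* endpoint would then partly reflect when rescue was given and who missed a sample, rather than glycaemic control at the end of the trial. If rescue use differs between arms, so does exposure to this error. The same sentence of the SAP keeps post-rescue values for weight.

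**Working it through.** The plan gives no figure on this point to reproduce. The check sets the rules side by side, applies them to examples, and then bounds the group affected.

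**1. How old the carried value can be.** The protocol flow chart schedules HbA1c at Visit 6 (week 16), Visit 7 (week 32) and every 16 weeks up to Visit 32 (week 432). Take a patient on the full schedule who is rescued just after Visit 7 and misses only the Visit 32 sample.

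- LOCF uses week 32, a value 432 − 32 = 400 weeks old. It ignores Visits 8 to 31, which is 31 − 8 + 1 = 24 measurements.
- LOCF-ROC uses Visit 31 (week 416), a value 432 − 416 = 16 weeks old.

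This is the extreme case. Patients randomised later have shorter follow-up.

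**2. Whether baseline can be reached.** Protocol Section 4.2.1 permits rescue from Visit 2. The first planned on-treatment HbA1c is at Visit 6. Rescue in titration can therefore precede any on-treatment HbA1c, and LOCF then returns baseline. The entry range in Protocol Section 3.3.2 starts at 6.5%, so baseline can be ≤ 7.0%.

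**3. Direction of the error.** Invented HbA1c series (%), last sample missing in each:

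| Case | Baseline | Before rescue | After rescue | LOCF | LOCF-ROC |
|---|---|---|---|---|---|
| A: rescue after a high HbA1c | 7.4 | 7.2, 7.4, 7.8 | 6.9, 6.8 | 7.8, non-responder | 6.8, responder |
| B: rescue in titration | 6.9 | none | 7.4, 7.5, 7.6, 7.6, 7.6 | 6.9, responder | 7.6, non-responder |
| C: rescue not prompted by HbA1c | 7.2 | 6.8, 6.9 | 7.5, 7.6, 7.6 | 6.9, responder | 7.6, non-responder |

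Case A fits rescue prompted by HbA1c > 7.5%. Cases B and C are possible because SAP Section 5.2.1 counts any increase in background dose and any new antidiabetic drug as rescue (insulin only if taken for at least 15 days), and Protocol Section 4.2.1 also allows a fasting-glucose trigger.

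**4. Key secondary composites.** Both require no rescue between Visit 6 and Final Visit (SAP Section 5.2.1). Rescue in that window is already a failure, so the choice of imputation changes nothing. Rescue begun only in titration is not expressly inside the window. A patient like case B could then enter a composite as a glycaemic success on the baseline value.

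**5. Size of the group affected.** The documents give neither rescue rates nor missing-HbA1c rates. Assume 3000 patients per arm (the planned number), with a share s = 60–80% on drug at the end, r = 20–60% of those rescued, and m = 1–10% of those lacking the last HbA1c. Patients scored by the rule = 3000 × s × r × m.

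- Low: 3000 × 0.6 × 0.2 × 0.01 = 3.6, about 4 (0.12%).
- Middle: 3000 × 0.8 × 0.4 × 0.05 = 48 (1.6%).
- High: 3000 × 0.8 × 0.6 × 0.10 = 144 (4.8%).

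These are patients scored on a pre-rescue or baseline value. Only some would change status, and opposite changes partly cancel.

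**The case against.** The strongest objection is that the full endpoint definition is not public. The word *overall* appears in one clause that points to Protocol Section 7.1, and the detailed tertiary endpoint text is missing from both public documents. The relevant heading in SAP Section 6.6 speaks of key secondary and tertiary binary endpoints, whereas Protocol Section 5.1.1 calls this one secondary. An exemption could sit in the unseen text, and its absence here is no fault of the plan. This stands as a limit: regardless of rescue is an inference from the contrast within the sentence, though the natural one.

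A second objection is that the split between HbA1c and weight is a deliberate convention. The treatment-emergent evaluation in SAP Section 7.5.2.2.1 generally drops post-rescue HbA1c and keeps post-rescue weight. That convention concerns the continuous analyses and does not justify the rule for a binary endpoint that ignores rescue.

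A reader might infer that the overall response rate is understated, and put numbers on it. With 2–10% missing, 30–50% of those rescued and 25–40% of those controlled after rescue, the product runs from 0.02 × 0.3 × 0.25 = 0.15 points to 0.10 × 0.5 × 0.4 = 2.0 points. With rescue at 30% in one arm and 50% in the other, the gap would be 0.10 × (0.5 − 0.3) × 0.4 = 0.8 points. The documents do not support this as a net bias. The formula counts only false non-responders, assumes that each had a failing pre-rescue value, and omits cases such as B and C. Its inputs are also assumptions. HbA1c is scheduled at every maintenance visit and at end of treatment, so 10% missing among patients still on drug may well be too high.

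Finally, little turns on it. The endpoint is outside the testing hierarchy, and SAP Section 7.5.2 treats such analyses as exploratory. That is correct and limits the weight of the point.

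**Conclusion.** The mismatch is real on the visible text. For the *overall* endpoint, a rescued patient still on drug who lacks only the last HbA1c is scored on a pre-rescue or baseline value, although measured post-rescue values exist and a method that uses them is already defined.

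Misclassification can go either way. False non-responders are probably more common where rescue followed HbA1c > 7.5%. False responders arise where the pre-rescue or baseline value was ≤ 7.0%. The net direction and size cannot be derived from the documents. The effect is probably small and falls mainly on an exploratory endpoint. The conclusion rests on reading *overall* as regardless of rescue and on there being no exemption in the text that is not public.

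A reader might also infer that the key secondary composites cannot be touched, so that a change would be neutral there. That holds for rescue after Visit 6. It is not established for rescue begun only in titration.

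**What to change.** In the binary-endpoint rule of SAP Section 6.6:

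- Use LOCF-ROC for HbA1c as already done for weight, at minimum for the *overall* endpoint.
- State that a baseline HbA1c is never used as the Final Visit value in a binary endpoint.
- State that a patient with no on-treatment HbA1c is a non-responder.

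The cost is a short SAP edit and one derivation flag; no new method is needed. If the change is applied to all binary endpoints, key secondary status may change for a few patients rescued before Visit 6. It should therefore be made and documented before unblinding.

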### **5.2 SECONDARY ENDPOINTS**

#### **5.2.1 Key secondary endpoints**

The key secondary efficacy endpoints are:

- time to the first occurrence of any of the following CEC confirmed adjudicated components of CV death (including fatal stroke and fatal MI), non-fatal MI (excluding silent MI), non-fatal stroke or hospitalisation for unstable angina pectoris  
This endpoint will be further referred to also as time to first 4-Point-MACE (4P-MACE).

To clarify: Silent MI is not an endpoint to be confirmed by adjudication. Any investigator reported silent MI that is adjudicated and confirmed as being an MI by the CEC will be counted as MI.

- composite endpoint of (treatment sustainability defined as the proportion of patients that are on study treatment at study end, that at Final Visit maintain glycaemic control ( $HbA1c \leq 7.0\%$ ) without need for rescue medication (between end of titration [Visit 6]

and Final Visit) and patients without any moderate/severe hypoglycaemic episodes (between Visit 6 and Final Visit) and without > 2% weight gain at Final Visit (between Visit 6 and Final Visit))

(A patient fulfilling all these criteria is considered a ‘responder’.)

- composite endpoint of (treatment sustainability defined as the proportion of patients that are on study treatment at study end, that at Final Visit maintain glycaemic control (HbA1c  $\leq$  7.0%) without need for rescue medication (between Visit 6 and Final Visit) and patients without > 2% weight gain at Final Visit (between Visit 6 and Final Visit)) (A patient fulfilling all these criteria is considered a ‘responder’.)

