#### Rescue medication in general:

Rescue medication is defined as any dose increase of anti-diabetic background medication (as compared to one day prior to first drug administration) or introduction of new anti-diabetic treatment, for insulin any new onset and intake for at least 15 days, starting from the date of first drug administration until the time as specified in [Section 6.8.3](#).

In general, any therapy with the start date equal to the date of first trial drug intake is considered as being taken after first trial drug intake.

If a patient switches to or adds protocol defined background medication at or after the date of first trial drug intake, this will be considered rescue medication. (The same applies for a change from metformin or alpha-glucosidase inhibitor to metformin + alpha-glucosidase inhibitor.)

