[Table 6.7.3: 1](#) shows the time windows for FPG, planned to be measured at every visit.

Table 6.7.3: 1 Time windows for visits for FPG

Visit number	Planned days after randomisation	Planned days on treatment	Time window start* based on planned days on treatment	Time window end* based on planned days on treatment
2	0	1	NA	1**
3	28	29	2	43
4	56	57	44	71
5	84	85	72	99
6	112	113	100	169
7	224	225	170	281
8	336	337	282	393
9	448	449	394	505
10	560	561	506	617
11	672	673	618	729
12	784	785	730	841
13	896	897	842	953
14	1008	1009	954	1065
15	1120	1121	1066	1177
16	1232	1233	1178	1289
17	1344	1343	1290	1401
18	1456	1457	1402	1513
19	1568	1569	1514	1625
20	1680	1681	1626	1737
21	1792	1793	1738	1849
22	1904	1905	1850	1961
23	2016	2017	1962	2073
24	2128	2129	2074	2185
25	2240	2241	2186	2297
26	2352	2353	2298	2409
27	2464	2465	2410	2521
28	2576	2577	2522	2633
29	2688	2689	2634	2745
30	2800	2801	2746	Study drug stop date + x days***

\*actual days on treatment

\*\*has to be pre-treatment value

\*\*\*The definition of x is endpoint specific, cf. [Table 6.7.2: 1](#).

As e.g. HbA1c and weight are not measured at every visit, the time windows until visit 6 would be as shown in [Table 6.7.3: 2](#) (from visit 7 on windows as described above apply):

Table 6.7.3: 2 Time windows until visit 6 for e.g. HbA1c and weight

Visit number	Planned days after randomisation	Planned days on treatment	Time window start* based on planned days on treatment	Time window end* based on planned days on treatment
2	0	1	NA	1**
6	112	113	2	170

\*actual days on treatment

\*\*has to be pre-treatment value

For further visits beyond visit 30 the same concept is applied.

Only one observation per time window will be selected for analysis at a visit – the value will be selected which is closest to the protocol planned visit day. If there are two observations which have the same difference in days to the planned day or if there are two observations on the same day, the first value will be used. If there are multiple values within the time window of the last visit, including a value on the last day of drug intake, the value on the last day of drug intake is used as the value of the last visit.

For LOCF imputation (including interpolation), the last observed on-treatment value will be carried forward, whether or not it was selected in the previous time window (see [Section 6.6](#)).

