#### Treatment-emergent evaluation

Patients with a baseline measurement and at least one on-treatment measurement will be included for analysis over time. Only values obtained until last permanent treatment stop will be considered. The assignment of values to be on-treatment is defined in [Table 6.7.2: 1](#).

In general, for the evaluation of HbA1c and FPG, for patients receiving rescue therapy all on-treatment efficacy measurement after the start of rescue therapy will not be used for analysis and hence set to missing (OC, LOCF). If a patient receives rescue therapy before the first available on-treatment measurement, this patient will not be included in the analysis, except for HbA1c LOCF analysis.

For total cholesterol, HDL cholesterol, LDL cholesterol, triglycerides, creatinine, urinary albumin, UACR, eGFR and weight values before and after rescue therapy intake will be considered (OC-ROC, LOCF-ROC).

In addition, analyses following the OC concept will be performed.

For the following parameters, only values obtained in the fasted state will be used for analyses: FPG, total cholesterol, HDL cholesterol, LDL cholesterol, triglycerides.

For UACR log10 transformed data will be used within the ANCOVA or respectively MMRM model, the results will be back-transformed to the original scale.

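### Key secondary endpoints 2 and 3: when the last on-treatment HbA1c is missing, a patient rescued during titration is normally judged on the pre-treatment baseline HbA1c

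*SAP*

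**What the plan says.** **Endpoints.** Under Protocol 7.1 and SAP 5.2.1, a responder for key secondary endpoints 2 and 3 is on study drug at study end, has HbA1c ≤7.0% at Final Visit "without need for rescue medication (between Visit 6 and Final Visit"), and has not gained more than 2% in weight since Visit 6. Endpoint 2 also requires no moderate or severe hypoglycaemia in that window.

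**Rescue.** SAP 5.2.1 defines rescue as a dose increase of background therapy or a new antidiabetic agent, "starting from the date of first drug administration". Protocol 4.2.1 permits rescue during titration for confirmed fasting glucose above 240 mg/dl.

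**Imputation.** The SAP 6.6 text on binary endpoints including HbA1c and/or weight covers a patient who did not permanently and prematurely stop treatment and whose value at the last on-treatment visit is missing. For that patient, "the missing value will be imputed by LOCF-ROC (weight)/LOCF (HbA1c").

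**The two methods.** Under LOCF, "Any values taken after rescue medication intake will be set to missing". For HbA1c there is one exception to the general rule against carrying baseline forward: "if a patient receives rescue therapy before the first available on-treatment HbA1c measurement, the HbA1c baseline value will be carried forward". LOCF-ROC keeps post-rescue values.

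**Timing.** The protocol flow chart schedules no HbA1c between Visit 2 and Visit 6 (week 16). SAP 6.7.3 reflects this in the table titled "Time windows until visit 6 for e.g. HbA1c and weight".

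**The concern.** The endpoint looks at rescue from Visit 6 on, whereas the LOCF rule looks at rescue from the first dose. A patient whose rescue began in titration can pass the endpoint's rescue criterion as written and still have every scheduled on-treatment HbA1c removed by LOCF, because the first of them comes after rescue. The value judged at Final Visit is then the one taken before treatment.

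For a continuous change from baseline, a carried-forward baseline reads as no change. Against a 7.0% threshold it can read as success, because entry HbA1c starts at 6.5% (Protocol 3.3.2). It cannot show that control was maintained on study drug. For patients who entered on a sulphonylurea or glinide it reflects a drug stopped at Visit 2. Within the same responder flag, weight would use post-rescue data and HbA1c would not.

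At stake are the fourth and fifth tests of the hierarchy, and the responder rates and odds ratios that SAP 7.5.1 plans to report.

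**Working it through.** The plan gives no rate or power for these two endpoints, so there is no figure to reproduce. The check follows the rules through and then sizes the result under assumed rates.

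**1. Who can be affected.** Take patients on drug at study end:

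| Rescue | Last on-treatment HbA1c | LOCF | LOCF-ROC | Can the choice matter? |
|---|---|---|---|---|
| None | Missing | Last observed | Last observed | No |
| Started from Visit 6 on | Either | Non-responder already | Non-responder already | No |
| Started before Visit 6 | Observed | Not imputed | Not imputed | No |
| Started before Visit 6 | Missing | Baseline | Last observed | Yes |

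The choice of LOCF over LOCF-ROC for HbA1c therefore acts only in the last row.

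**2. What it does there.** Two hypothetical patients, both rescued on day 60, last HbA1c missing:

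- Baseline 6.8%, last observed 7.6%. LOCF gives 6.8%, criterion met. LOCF-ROC gives 7.6%, not met.
- Baseline 8.0%, last observed 6.7%. LOCF gives 8.0%, not met. LOCF-ROC gives 6.7%, met.

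The error can go either way.

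**3. How many.** N = 6000 (Protocol synopsis). Assumptions, not in the documents:

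- f, share rescued before Visit 6 and on drug at study end: 0.5-3%.
- m, share of those with the last HbA1c missing: 2-10%.

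Judged on baseline = N × f × m:

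- Low: 6000 × 0.005 × 0.02 = 0.6
- High: 6000 × 0.03 × 0.10 = 18

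**4. How many wrongly classed on HbA1c.** Let b be the share with baseline ≤7.0% and r the share truly ≤7.0% at Final Visit, taken as independent. Apply the entry ranges of Protocol 3.3.2 to baseline, with a uniform spread (an assumption). Then b = 0.5/2.0 = 0.25 over 6.5-8.5%, and b = 0.5/1.0 = 0.50 over 6.5-7.5%. Assume r = 0.2-0.4.

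Wrong share = b(1 − r) + (1 − b)r:

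- b = 0.25, r = 0.2: 0.20 + 0.15 = 0.35
- b = 0.25, r = 0.4: 0.15 + 0.30 = 0.45
- b = 0.50, any r: 0.50

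Wrong HbA1c status: 0.6 × 0.35 = 0.2 up to 18 × 0.50 = 9 patients, both arms together.

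**5. Ceiling on the arm difference.** If all 9 fell in one arm of 3000, in one direction, and all met every other criterion, the responder rate would shift by 9/3000 = 0.30 points. At an assumed 20% responder rate, the SE of the difference is √(2 × 0.2 × 0.8/3000) = 1.03 points, so the shift is about 0.3 SE. If the errors balance between arms, the difference does not move.

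**The case against.** **Rescue still in use after Visit 6 may already count.** The criterion speaks of need for rescue, and a patient still taking a rescue agent after Visit 6 can fairly be said to need it. The Protocol 7.1 footnote counts any dose increase or new agent during study treatment, with no Visit 6 start. If ongoing rescue counts, those patients fail whatever their HbA1c, and only patients whose early rescue ended before Visit 6 remain exposed. This stands as an open point: the SAP defines rescue by its onset and does not say how rescue begun earlier and still ongoing is treated.

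**The Final Visit derivation cannot be checked.** SAP 5.2.1 refers it to SAP 7.5.1, and it does not appear in the public text of that section. It may deal with these patients.

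**The group is small.** Titration rescue for hyperglycaemia needs confirmed fasting glucose above 240 mg/dl, in patients who entered with HbA1c no higher than 8.5%. An HbA1c that stays above 7.5% would usually prompt further treatment, which is rescue and a failure. Both are fair. A false success, however, needs only later values above 7.0%, and values between 7.0% and 7.5% do not meet the HbA1c criterion for rescue.

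**Some of the difference is intended.** SAP 7.5.2.2.1 also analyses HbA1c without post-rescue values and weight with them. Failing a patient controlled only by continuing rescue may be what the endpoint means. If so, the rescue criterion should do that work. A baseline value does not, since it passes a patient who started at 6.8%.

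**An unscheduled HbA1c before rescue** would be carried forward instead of baseline. That is correct, but it would still be a titration-phase value standing in for Final Visit.

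**A stronger reading is tempting.** Table 6.6: 1 replaces values after rescue and adds that "If no on-treatment HbA1c measurement prior to rescue therapy is available baseline values are carried forward". SAP 7.5.2.2.1 says that "all on-treatment efficacy measurement after the start of rescue therapy will not be used for analysis and hence set to missing". A reader might infer that even an observed Final Visit HbA1c is discarded, so that every patient rescued in titration (6000 × 0.5-3% = 30-180) is judged on baseline. The documents do not support this. The table row concerns HbA1c at each visit and change from baseline, SAP 7.5.2.2.1 is headed for continuous endpoints, and the binary endpoints have their own text, which fills only a missing value.

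**Conclusion.** The point holds in a limited form. As written, the SAP 6.6 rule normally substitutes a pre-treatment HbA1c for the Final Visit value in one group: patients rescued in titration, not otherwise non-responders, who did not stop treatment permanently and prematurely and whose last on-treatment HbA1c is missing. In that group the 7.0% criterion can be wrong in either direction although later values were observed.

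Under the assumed rates, about 1-18 of 6000 patients are judged on baseline and 0-9 get a wrong HbA1c status. Fewer get a wrong responder status if some fail on weight or, for endpoint 2, on hypoglycaemia. The count scales with the product of two unknown rates: at 5% and 20% it would be 6000 × 0.05 × 0.20 = 60 judged on baseline.

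A reader might also infer a bias towards one arm. The documents give no basis for that. The primary analysis and the first key secondary endpoint are untouched. Severity: minor.

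**What to change.** In the SAP 6.6 text on binary endpoints including HbA1c and/or weight, for key secondary endpoints 2 and 3, replace the LOCF label for HbA1c with: *LOCF-ROC (HbA1c), using on-treatment values from Visit 6 on; if there is none, non-responder*.

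Add one sentence stating whether rescue begun before Visit 6 and still ongoing after it counts as rescue for these endpoints. That choice is the sponsor's. If it counts, the programming needs the stop date of early rescue.

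The cost is one label and one sentence before unblinding. LOCF-ROC is already planned for HbA1c in SAP 7.5.2.2.1. The non-responder fallback is in keeping with the worst-case handling that Protocol 7.4 applies to binary endpoints after premature discontinuation. The change can alter results only for patients rescued before Visit 6.
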